# 10.3 Method of statistical analysis in relation to objectives

If nothing else is stated, descriptive statistics will be given for each variable in the study and p-values may be complemented by confidence intervals as appropriate.

# 10.3.1 Primary objective

The primary objective is prosthetic survival 1 year after permanent restoration. The design of the study is a single group study with success/failure reported for the primary variable for each subject. The aim is to estimate the proportion of subjects with "success"  $(\pi)$ . The hypotheses of interest are:

H0:  $\pi \le \pi_0 \ (\pi_0=90 \ \%)$ 

 $H_1$ :  $\pi > \pi_0 (\pi_0=90 \%)$ 

Limit to be tested against is: Ho: 90 %

The null hypothesis will be rejected if the two-sided p-value is less than  $\alpha$  (0.025). A p-value

(one-sided) below 2.5 % is considered statistically significant.

The p-value will be calculated using the Binomial test and a two sided exact binomial 95% confidence interval will also be presented.

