# 10.4 Determination of sample size

In this study, subjects will receive single crown restorations and the primary objective is prosthetic survival one year after permanent restoration. Studies reporting on implant-supported single crowns found in the literature  $^{17-20}$ , show a prosthetic survival rate of 96.3% (95% CI: 94.2–97.6%) after 5 years. Following this, the expected true prosthetic survival rate, after one year, is set to 97% (= $\pi$ 1).

The aim is to estimate the proportion of subjects with "success". The hypotheses of interest are

 $H_0$ :  $\pi$  ≤  $\pi_0$  and  $H_1$ :  $\pi$  >  $\pi_0$ 

Limit to be tested against H0: 90 %. The null hypothesis will be rejected if the two-sided p-value is less than  $\alpha$  = 0.025 and if  $\pi$  =  $\pi$ 1 (97%) the power to reject H0 should be 90 %.

The formula to calculate the sample size is (n is the number of fully evaluable subjects)

$$n = \left[ \frac{\lambda_{\alpha} \sqrt{\pi_0 (1 - \pi_0)} + \lambda_{1 - \beta} \sqrt{\pi_1 (1 - \pi_1)}}{\pi_0 - \pi_1} \right]^2$$

In the formula  $\lambda_x$  is the x:th quintile of the standardized normal distribution.

As it is a one-sided hypothesis:

$$\alpha$$
 = 2.5 %  $\lambda_{\alpha}$ = 1.9600  $\beta$  = 90 % then  $\lambda_{1\text{-0.90}}$  0 1.2816.

Given the assumptions above the sample size is estimated to include 133 evaluable subjects with a power of approximately 90 %.

Assuming a subject drop-out rate of 15 % a total of 157 (=133/0.85) is expected to be included in the study.

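### The primary rejection rule is given as both a two-sided and a one-sided p-value below 0.025; read two-sided, 133 subjects give about 79% power instead of the stated 90%.

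*Combined protocol and SAP*

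**What the plan says.** Section 10.3.1 sets directional hypotheses, H0: π ≤ 90% against H1: π > 90%, for the proportion with prosthetic survival at 1 year ("Limit to be tested against is: Ho: 90" %). It then gives two decision rules in consecutive sentences:

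- "The null hypothesis will be rejected if the two-sided p-value is less than" α, with α given as 0.025.
- A p-value described as "one-sided) below 2.5 % is considered statistically significant".

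The test is the binomial test, and a two-sided exact 95% confidence interval is to be reported with it.

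Section 10.4 repeats the two-sided sentence with α = 0.025. It then introduces the sizing with "As it is a one-sided hypothesis" and uses α = 2.5% with a normal quantile of 1.9600. It concludes: "Given the assumptions above the sample size is estimated to include 133 evaluable subjects with a power of approximately 90" %.

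Section 10.3.2 applies the primary analysis to prosthetic survival at 3 and 5 years. Section 10.1 makes a separate statistical analysis plan optional.

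**The concern.** The two sentences define different tests. A one-sided p-value below 0.025 allows 2.5% in the upper tail. A two-sided p-value below 0.025 allows about 1.25% there, which is a stricter criterion. The sample size and the reported 95% interval match only the first.

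The stake is the verdict on the primary objective. If the rules part at a result the trial could well produce, the plan supports both a claim of success and a finding of failure, and the choice would be made after seeing the data. The stated power also depends on which sentence is applied. Because a separate analysis plan is optional, these sections may be the only prespecified rule, and section 10.3.2 carries the ambiguity into the 3- and 5-year tests.

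**Working it through.** **Inputs.** π0 = 0.90 and the exact binomial test (10.3.1); π1 = 0.97 (10.4: "the expected true prosthetic survival rate, after one year, is set to 97" %); 133 evaluable subjects, 90% power and 15% drop-out (10.4).

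**1. The plan's own figure.** The formula in 10.4 is

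n = [(z_α √(π0(1−π0)) + z_power √(π1(1−π1))) / (π0 − π1)]²

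Here √(0.90 × 0.10) = 0.3 and √(0.97 × 0.03) = 0.1706. With z_α = 1.9600 and z_power = 1.2816:

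n = [(0.5880 + 0.2186) / 0.07]² = 132.78, so 133; and 133/0.85 = 156.5, so 157.

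The plan's numbers reproduce, and they rest on one-sided 2.5%.

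**2. The same formula under the two-sided sentence.** A two-sided 0.025 puts 0.0125 in the upper tail, so z_α = 2.2414:

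n = [(0.6724 + 0.2186) / 0.07]² = 162.03, so 163; and 163/0.85 = 191.8, so 192.

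The normal-approximation power at n = 133 is Φ[(0.07√133 − 0.3 z_α) / 0.1706]. This is 90.1% with 1.9600 and 78.5% with 2.2414.

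**3. Exact binomial at n = 133.** Let F be the number of failures. The one-sided p-value at f failures is P(F ≤ f) with failure probability 0.10. Power is the same sum, up to the largest f that rejects, with failure probability 0.03.

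| Rule | Rejects with | Upper-tail error at π = 90% | Power at π = 97% |
|---|---|---|---|
| One-sided p < 0.025 | ≤ 6 failures (≥ 127/133) | 0.0172 | 89.4% |
| Two-sided p < 0.025 | ≤ 5 failures (≥ 128/133) | 0.0066 | 78.9% |

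The protocol does not say how a two-sided exact p-value would be formed. At n = 133 the cut-off is the same whether the tail is doubled or the minimum-likelihood method is used.

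**4. Where the rules disagree.** At 127/133 (95.5%):

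- one-sided p = 0.0172: reject;
- two-sided p = 0.0343 (doubled) or 0.0300 (minimum likelihood): do not reject;
- lower limit of the exact 95% interval = 90.4%, above 90%, which agrees with the one-sided rule.

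The chance of exactly 6 failures in 133 is 10.4% at a true rate of 97%, and about 16% at 96% or 95%.

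**5. Other evaluable numbers.** The exact test moves in steps, so the gap varies with n. Using the doubled p-value, the cut-offs coincide at 138 to 140 and at 152 to 153. They differ by one failure at every other n from 127 to 157.

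**The case against.** The strongest reply is that the intended rule is easy to infer. The hypotheses are directional, the sizing is declared one-sided with 1.9600, the 95% interval has a 2.5% lower tail, and 133 reproduces only on that basis. The one stock sentence that says two-sided, used twice, is the odd one out. This stands as a reading of intent, and it means the study is not undersized for the rule it was sized on. It does not settle the matter, because the stray wording sits in the rejection rule itself, in both sections that define the primary test, and no text gives either sentence precedence.

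Three narrower points also stand:

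- **No inflation of type I error.** The two-sided rule is the stricter one. Even if the lenient rule were chosen after the fact, the error at n = 133 is 1.7%, below 2.5%. The harm is an undetermined verdict.
- **The 79% belongs to n = 133.** The evaluable number will probably differ, and at a few sizes the rules agree. At most sizes from 127 to 157 they do not, and the final number is not known in advance.
- **163 is a normal-approximation figure.** Under the exact test, the two-sided rule gives 88.1% power at 163 but 91.2% at 152, because exact power rises and falls with n. The 163 and 192 show what the plan's own formula returns and are not a recommended size.

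**Conclusion.** The inconsistency is real and affects the primary conclusion. With 133 evaluable subjects, the two rules differ by one permitted failure and give opposite answers at 127/133. Power at a true rate of 97% is 89.4% under the one-sided rule and 78.9% under the two-sided rule. The claim of "133 evaluable subjects with a power of approximately 90" % is sound for the first and wrong for the second by about 11 percentage points.

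These figures assume the exact binomial test named in 10.3.1, exactly 133 evaluable subjects, and the plan's values of 90% and 97%. The shortfall in power arises only if the two-sided sentence is applied as written. The text should be corrected before the 1-year data are analysed.

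**What to change.** In sections 10.3.1 and 10.4, delete the sentences that reject on a two-sided p-value below 0.025, and state one rule in both places: H0 is rejected if the one-sided exact binomial p-value is below 0.025, equivalently if the lower limit of the two-sided exact (Clopper-Pearson) 95% confidence interval exceeds 90%. This keeps the rule the study was sized on, agrees with the interval already planned, and avoids having to define a two-sided exact p-value. Section 10.3.2 then inherits a single rule for years 3 and 5.

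It would help to add that, with 133 evaluable subjects, the rule rejects with at most 6 failures and has exact power of 89%, and that the cut-off will be recalculated for the evaluable number actually reached.

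The cost is a wording change in two sections. The targets of 133 evaluable and 157 enrolled stay as they are. The change should be dated before the 1-year partial clean file in section 10.5. If that point has passed, the report should say so and give the result under both rules.

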### 10.3.2 Secondary objectives

Prosthetic survival 3 and 5 years after permanent restoration.

Analysis equivalent to primary objective will be performed.

Evaluate implant survival rate up to 5 years after permanent restoration.

Proportion of survived implants will be calculated.

A two sided exact binomial 95% confidence interval for the proportion of lost implants will be calculated.

Marginal bone levels alteration up to 5 years after permanent restoration

The measured aspects/sides as well as implants mean value will be presented and used in analysis. Descriptive statistics for absolute values and the change from baseline (Visit 5; Permanent Restoration) will be calculated, in addition the marginal bone level change from implant placement may be calculated. Analysis of the change over time using the Wilcoxon Signed Rank test will be included

Condition of the peri-implant mucosa.

Descriptive statistics will be presented and analysis over time will be included.

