# 4 Study design

# 4.1 Overall study design

A prospective, non-controlled, multicentre study on the Acuris-conometric concept. The study comprises a 5 year follow-up from baseline, permanent restoration, and includes 11 visits. Each subject will receive one single implant placed in position 17-27 or 37-47 to support a single restoration. The implant will be placed in fresh extraction socket or healed ridge using one- or two-stage surgical protocol, immediate or conventional loading. The permanent restoration must be in place within six months after implant surgery at the latest. A conometric abutment will be used for the prosthetic restoration. The final crown will be cemented onto the final cap extraorally and fixated on the conometric abutment using retention mode.

The sample size estimation shows that 133 fully evaluable subjects are needed to fulfill the primary objective. Given an assumed drop-out rate of 15 % the aim is to include 157 subjects in total, see section 10.4 "Determination of sample size" for details.

However, if the drop-out rate is lower or higher than the estimated level, the number of enrolled subjects may be adjusted in order to reach the 133 fully evaluable subjects.

It is expected that the study will include 9 study sites and that each study site will enroll approximately 15-20 subjects using the Acuris-conometric concept on the implant systems; Ankylos, Astra Tech Implant System or Xive. Each site will use only one implant system.

The overall study design is presented in Appendix B: Visit and procedure plan.

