# 5.5 Discontinuation of subjects from study

### 5.5.1 Criteria for discontinuation

Subjects may be discontinued from the study at any time. Specific reasons for discontinuing a subject may include:

- Voluntary discontinuation by the subject who is free to at any time discontinue his/her participation in the study, without prejudice to further treatment.
- Safety reasons as judged by the Investigator or Dentsply Sirona Implants.
- Severe non-compliance to the CIP as judged by the Investigator and/or Dentsply Sirona Implants.
- Incorrect enrollment, i.e. a subject did not to meet the required inclusion/exclusion criteria for the study, but nevertheless was enrolled (see section 5.3.3 Subject-selection criteria).
- Subject lost to follow-up (as defined by the inability to reach the subject after 3 attempts to contact him/her e.g. by phone, e-mail or letter; all should be documented in the subject's medical records).
- Loss of the study implant. (If a new implant is placed, the new implant should not be recorded in the eCRF.)
- Subjects in need of replacement of existing Investigational Product (IP) (abutment or final cap) after Permanent Restoration (PR).
  - Removal of existing IP after PR for adjustments (e.g. maintenance, polish, esthetic adjustments of crown) is not reason for discontinuation.
  - A loose abutment screw, is not reason for discontinuation if replacement of the abutment screw is possible without changing the abutment.

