#### 6.3.2.2 Implant survival

Implant survival rate up to five years after permanent restoration (number of implants in situ). Any implant that is removed or lost after permanent restoration will be considered an implant loss, whatever the reason for removal.

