### 10.1.3 Handling of dropouts and missing data

Subjects dropping out from the study during the recruitment period will be replaced. Subjects dropping out after completion of the recruitment period will not be replaced but compensated for in the sample size estimation, see Section 10.4 Determination of sample size. Dropouts will be analyzed as described in Section 10.2 Description of analysis sets.

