## 10.2 Description of analysis sets

The study will be analyzed using a Safety (S) and a Per Protocol (PP) population approach. The S analysis set will consist of all enrolled subjects where any safety parameters, study specific procedures or study specific measures were performed and/or collected. Safety events will be divided and presented as two different groups depending on when the safety event started:

- 1. Pre-Permanent Restoration delivery: Safety events with start date prior to Permanent Restoration i.e. the period from Implant installation up to Permanent Restoration delivery date.
- 2. Post permanent delivery: Safety events with start date same as or after Permanent Restoration delivery i.e. Permanent Restoration delivery until end of study.

The PP analysis set will consist of all subjects fulfilling the inclusion criteria, none of the exclusion criteria and have been treated in accordance with the CIP, e.g. have an implant placed and the final permanent restoration within six months after implant placement, according to Acuris-conometric concept. Treatment efficacy related conclusions will be based on the results from the PP analysis.

All subject data will be included in subject data listings.

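### Section 10.3.2 analyses 3- and 5-year prosthetic survival and implant survival as binomial proportions with no rule for unknown status; Kaplan-Meier would be a cheap improvement, worthwhile mainly at 5 years

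*Combined protocol and SAP*

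**What the plan says.** Section 10.3.1 analyses 1-year prosthetic survival with a binomial test against 90% and a two-sided exact 95% interval. Section 10.3.2 carries this to years 3 and 5: "Analysis equivalent to primary objective will be performed". Implant survival up to 5 years is a simple proportion: "A two sided exact binomial 95% confidence interval for the proportion of lost implants will be calculated". No time-to-event method appears in the plan.

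Section 10.4 assumes 15% drop-out, without a time horizon. On losses after recruitment, section 10.1.3 says "Subjects dropping out after completion of the recruitment period will not be replaced but compensated for in the sample size estimation", and then "Dropouts will be analyzed as described in Section 10.2 Description of analysis sets". Section 10.2 defines a Safety set and a Per Protocol set and adds "Treatment efficacy related conclusions will be based on the results from the PP analysis". The Per Protocol set is defined by eligibility and treatment, not by known status at year 3 or 5.

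Under section 5.5.1, loss of the study implant and the need to replace the abutment or final cap are both reasons to discontinue. Section 6.3.1.2 classes loss of retention and loss or fracture of the abutment as prosthetic failure. Section 6.3.2.2 says "Any implant that is removed or lost after permanent restoration will be considered an implant loss, whatever the reason for removal".

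**The concern.** Over five years some subjects will leave with a working restoration and no later assessment. A proportion at a fixed time needs a rule for them, and the cross-reference from section 10.1.3 does not lead to one. Section 4.1 says "The sample size estimation shows that 133 fully evaluable subjects are needed to fulfill the primary objective", which suggests that subjects without a status are left out. A proportion built that way keeps failures seen before drop-out but discards the event-free follow-up of those who left. It is therefore slightly low and less precise than the collected data allow.

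Known failures also lead to discontinuation, and the plan does not say outright that these subjects stay in the later denominators.

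These are secondary analyses, but the study is titled a 5-year follow-up, and section 10.5 bases separate 3- and 5-year publications on them.

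**Working it through.** **The plan's own figure.** Section 10.4: n = [(1.9600·√(0.90·0.10) + 1.2816·√(0.97·0.03)) / 0.07]² = 132.8, so 133; 133/0.85 = 156.5, so 157. Both reproduce. No sample size or power is given for years 3 or 5.

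**Inputs.**
- From section 10.4: limit 90%, one-sided 2.5%, literature 5-year survival 96.3%, drop-out 15%.
- Assumed: constant hazards; independent drop-out of D = 15% by year 5, with 25% as an upper case; 157 restored subjects, with 133 as a low case because 157 is the number included and not the number restored.

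**Bias of the evaluable-only proportion at 5 years.** Let λ = −ln(S)/5 and μ = −ln(1−D)/5. Observed failures are F = λ/(λ+μ)·(1−e^(−5(λ+μ))), known survivors are C = e^(−5(λ+μ)), and the proportion estimates C/(C+F).
- S = 0.963, D = 15%: C = 0.963·0.85 = 0.8186, F = 0.0342, ratio 0.9599 (0.3 points low).
- S = 0.963, D = 25%: C = 0.963·0.75 = 0.7223, F = 0.0322, ratio 0.9573 (0.6 points low).
- S = 0.90: ratios 0.8922 and 0.8857 (0.8 and 1.4 points low).

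**Chance of a 5-year lower limit above 90% at a true 96.3%.** Simulated with censoring at the last attended visit (0, 0.5, 1, 2, 3, 4, 5 years), a log-log interval for Kaplan-Meier, and the exact interval when there are no events. Failures after the last attended visit are taken as unseen.

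| Restored | Drop-out | Evaluable-only | Kaplan-Meier | Gain (points) |
|---|---|---|---|---|
| 157 | 15% | 72.2% | 78.1% | 5.9 |
| 157 | 25% | 61.0% | 73.6% | 12.6 |
| 133 | 15% | 61.5% | 68.1% | 6.6 |
| 133 | 25% | 50.8% | 62.3% | 11.5 |

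I reran this with failures between the last visit and drop-out counted as seen. The levels fell by one or two points, and the gains were 6.1, 13.3, 6.5 and 11.6. Rounded, the gain is 6-7 points at 15% and 11-14 at 25%.

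**Lower drop-out.** At 5%, with continuous censoring, the figures are 79.8% against 79.7% (157) and 71.9% against 71.7% (133), so there is no gain. My rerun with visit censoring put Kaplan-Meier 0.3 points lower with 157 and 2 points lower with 133.

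**Three years** (true 97.8% on the same hazard, visit censoring). With 157: 97.4% to 97.9% at 15% and 95.4% to 96.7% at 25%. With 133: 93.6% to 93.7% and 90.0% to 92.7%.

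**One-sided error at a true 90%, 5 years, visit censoring.** About 0.006-0.009 evaluable-only and 0.012-0.014 Kaplan-Meier, both below 0.025.

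**Reach of the missing rule.** Take 157 restored, 133 with known status and 5 failures among them. Leaving unknowns out gives 128/133 = 96.2% (lower limit 91.4%). Counting them as survivors gives 152/157 = 96.8% (92.7%). Counting them as failures gives 128/157 = 81.5% (74.6%). The last is an extreme bound, not a forecast.

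**The case against.** The strongest reply is that the real gap is the missing unknown-status rule. One sentence would close it with the exact test kept, and that sentence would also serve the 1-year primary analysis. On this view Kaplan-Meier is a preference. Much of this stands: the rule comes first, the bias is small, part of the power gain comes from the discreteness of the exact test, and the gain is negligible at 3 years or with low drop-out. What remains is a moderate 5-year gain from data already collected.

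Three stronger readings are tempting, and the material does not support them.

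- *The choice of method would reverse the conclusion.* With 157 restored, 7 failures and 24 unknown, each spread evenly over 5 years, the evaluable-only lower limit is 89.5% (126/133). Kaplan-Meier reaches 90.1% only if censoring times are continuous. With censoring at the last visit, as recommended here, it is 89.96% and also misses 90%.
- *The plan drops known failures and so overstates survival.* Sections 6.3.1.2, 6.3.2.1 and 6.3.2.2 count lost retention, abutment loss or fracture, and any implant removed after restoration as failures, and they read most naturally as cumulative. Upward bias is a risk only if attendees alone were counted.
- *The plan prescribes an evaluable-only analysis with 15% lost by year 5.* The evaluable wording concerns the primary sample size, and the 15% has no horizon. It may include losses before restoration, so applying it again to 133 restored subjects may count it twice. That makes 133 a pessimistic case.

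**Conclusion.** The point holds as a cheap improvement to secondary analyses, with moderate confidence. The documents establish that the method is a plain proportion, that drop-out is expected, and that no rule covers unknown status. The size rests on assumptions outside the plan: an evaluable-only denominator, constant hazards, and independent drop-out of 15-25% by year 5. On these, the 5-year estimate is 0.3-0.6 points low at a true 96.3%, and Kaplan-Meier adds about 6-7 points of power at 15% drop-out or 11-14 at 25%. Because the evaluable-only test is conservative, a reader should not infer that the plan risks a false claim of survival above 90%.

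**What to change.** In section 10.3.2, or in the separate analysis plan that section 10.1 allows, and before the 3-year data are examined:

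- Estimate 3- and 5-year prosthetic survival and implant survival by Kaplan-Meier from the permanent restoration date, with a log-log 95% interval. Compare the prosthetic lower limit with 90%.
- Count every observed failure as an event at its first occurrence, including failures that lead to discontinuation under section 5.5.1. Censor other subjects at the last visit with known status.
- Keep the exact binomial interval as supportive, with a stated denominator: observed failures by that time point plus subjects with known status then. Report it when no event is observed, because the log-log interval is then undefined. For implant survival this has a probability of about 5-54% at an assumed 98-99.5% 5-year rate and 15% drop-out.
- Add a sensitivity analysis with all unknowns as failures and all as survivors. Include implants whose follow-up ends at component replacement, where censoring may be informative.
- State the unknown-status rule in section 10.1.3 or 10.2, so that the cross-reference leads to it.

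The cost is a few sentences, a little more analysis work, and reliance on non-informative censoring. No new data should be needed: section 6.4.2 collects event start dates and lists implant loss, abutment loss, abutment fracture and loss of retention among adverse device effects.
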